#### Liver Function Parameters

Participants with elevated post-baseline Alanine Aminotransferase (ALT), Aspartate Aminotransferase (AST) or Total Bilirubin that fall into these categories are identified. Number and percentage of these participants are tabulated. The summaries are presented based on categories of the liver function parameters summarised below in [Table 5](#).

**Table 5: Liver function parameters**

Liver Function Parameters	Category
ALT	

• <math>\geq 3 \times - \leq 5 \times</math> ULN

• <math>> 5 \times - \leq 8 \times</math> ULN

• <math>> 8 \times</math> ULN

AST	

• <math>\geq 3 \times - \leq 5 \times</math> ULN

• <math>> 5 \times - \leq 8 \times</math> ULN

• <math>> 8 \times</math> ULN

Total bilirubin	

• <math>\geq 2 \times - \leq 3 \times</math> ULN

• <math>> 3 \times - \leq 5 \times</math> ULN

• <math>> 5 \times - \leq 10 \times</math> ULN

• <math>> 10 \times</math> ULN

ALT or AST	

• <math>\geq 3 \times - \leq 5 \times</math> ULN

• <math>> 5 \times - \leq 8 \times</math> ULN

• <math>> 8 \times</math> ULN

Potential Hy's law	

• (AST <math>\geq 3 \times</math> ULN or ALT <math>\geq 3 \times</math> ULN) and (Total Bilirubin <math>\geq 2 \times</math> ULN)a

Liver Function Parameters	Category
---------------------------	----------

ALT = Alanine transaminase; AST = Aspartate transaminase; ULN: =upper limit of normal range.

a It includes all participants who have ALT or AST $\geq$ 3xULN and total bilirubin (BILI)  $\geq$ 2xULN, and in which the elevation in transaminases precede or coincide with (that is, on the same day as) the elevation in BILI. Hy's law is potential Hy's law, where no other reason, other than IMP, can be found to explain the combination of increases.

#### 4.2.1.3.2 Presentations

The changes in each laboratory parameter from baseline to each post-baseline visit are summarised graphically.

Laboratory abnormalities occurring from the start of IP administration to the last assessment on study as well as CTC grades are presented in listings together with further information about individual laboratory assessments. Worst toxicity grade, rates of grade 3-4 toxicity, and grade shifts of 2 or more from baseline to the maximum grade are presented. Summaries indicating hyper- and hypo- directionality of change are produced, where appropriate. Laboratory parameters that cannot be graded via NCI CTCAE are summarised with frequencies of post-baseline laboratory values categorized as low (L), normal (N), or high (H) using laboratory normal ranges compared to baseline.

Boxplots may be used to summarize changes in clinical laboratory results at each timepoint if the results are deemed of interest to present.

Chemistry and Haematology clinically significant on-treatment values worse than baseline will be presented. All clinically significant on-treatment values that were originally normal at baseline will be presented. On-treatment clinically significant values that were also clinically significant at baseline will be presented if CTCAE grade is higher than baseline, or if the clinically significant value is a change in direction (i.e. changed from clinically significant low value at baseline to clinically significant high value post baseline).

Listings are provided for all laboratory results.

#### Liver Function Parameters

Number and percentage of participants with elevated post-baseline ALT, AST or Total Bilirubin are tabulated. Individual participant data where elevated ALT or AST plus total bilirubin fall into the “Potential Hy's law” are summarised and/or listed.

A scatter plot of ALT versus total bilirubin, both expressed as multiples of the upper limit of normal (ULN), will be produced with reference lines at 3 $\times$ ULN for ALT, and 2 $\times$ ULN for total bilirubin. The scatter plot will be repeated for AST versus total bilirubin with reference lines at 3 $\times$ ULN for AST, and 2 $\times$ ULN for total bilirubin. In each plot, total bilirubin will be in the vertical axis. Liver biochemistry test results over time for patients who show elevated

ALT or AST ( $\geq 3$ xULN) and elevated total bilirubin ( $\geq 2$ xULN) (elevated results do not need to be present at the same visit), or a total bilirubin of  $\geq 5$ xULN will be tabulated and plotted.

#### **4.2.1.4 Clinical Laboratory, Urinalysis**

##### **4.2.1.4.1 Definitions and Derivations**

Laboratory parameters are assessed at baseline as well as throughout the study.

CTC grade is calculated for urinalysis at each visit. Maximum on treatment CTC is also calculated. Absolute values are compared to the local laboratory reference range and classified as low (below range), normal (within range or on limits of range) and high (above range). All values classified as high or low are flagged in the listings.

##### **4.2.1.4.2 Presentations**

For urinalysis, shift from baseline to worst on treatment results are presented. Urinalysis abnormalities occurring from the start of IP administration to the last assessment on treatment are presented.

Urinalysis clinically significant on-treatment values worse than baseline will be presented. All clinically significant on-treatment values that were originally normal at baseline will be presented. On-treatment clinically significant values that were also clinically significant at baseline will be presented if CTCAE grade is higher than baseline.

Listings are provided for urinalysis.

#### **4.2.1.5 Other Laboratory Evaluations**

##### **4.2.1.5.1 Definitions and Derivations**

##### **Pregnancy testing**

Pregnancy tests are obtained at baseline and at day 1 of each cycle.

##### **4.2.1.5.2 Presentations**

##### **Pregnancy testing**

Any pregnancy tests that result in a positive result are line listed by time-point at which the positive pregnancy result occurred.

#### **4.2.1.6 Vital Signs**

##### **4.2.1.6.1 Definitions and Derivations**

Vital sign parameters (body temperature, blood pressure, heart [pulse] rate, respiration rate, and body weight) are assessed at baseline and throughout the study.

#### 4.2.1.6.2 Presentations

Vital signs are summarised by study visit which may include descriptive statistics for the value of the parameters and the changes from baseline. Absolute values and change from baseline for vital signs data at each timepoint are presented using box plots.

Listings are also provided for vital signs using the normal ranges in [Table 6](#).

**Table 6 Vital Signs Normal Ranges**

AZ Test Name	Outside AZ defined reference range lower limit if	Outside AZ defined reference range upper limit if	AZ Unit
Diastolic blood pressure	<40	>110	mm Hg
Pulse	<40	>160	beats/min
Systolic blood pressure	<70	>180	mm Hg
Temperature	<35	>38	° C
Weight	<40	>130	kg

#### 4.2.1.7 Electrocardiogram

##### 4.2.1.7.1 Definitions and Derivations

ECG parameters are assessed at baseline as well as throughout the study. ECG parameters include heart [pulse] rate, RR, PR, QRS, QT and QT interval corrected using Fridericia's formula (QTcF). The QTcF is considered as the primary correction method to assess participant cardiac safety.

ECGs are performed at scheduled timepoints pre-dose and post-dose in single at on treatment visits and in triplicate at SCR and EOT. For triplicate measurements, the mean value of the triplicate measurement are recorded as the value of appropriate timepoint for pre-dose respective post-dose assessment. A triplicate measurement is only deemed missing where all triplicate values are missing, otherwise, if one value is missing the mean is taken from the two obtained measurements, and if two values are missing the value is taken as the one obtained measurement.

From the resting 12-lead ECGs values of the QT and RR intervals, the QTcF is derived using the following formula:

$$QTcF = \frac{QT}{RR^{\frac{1}{3}}}$$

where RR is in seconds.

The values of QTcF (milliseconds) are re-derived from the values of RR and QT during the creation of the reporting database.

The notable ECG interval values while on treatment are:

- Maximum QTcF intervals > 450 milliseconds, > 480 milliseconds, and > 500 milliseconds.
- Maximum changes from baseline in QTcF > 30, >60, and > 90 milliseconds.

#### 4.2.1.7.2 Presentations

ECG parameters are summarised using descriptive statistics by visit and change from baseline in ECG endpoints are calculated for each post-dose visit. Absolute values and change from baseline for ECG data at each timepoint are presented using box plots.

The number and percentage of participants having notable ECG interval values while on treatment are summarised.

Further, QT and QTcF intervals, at any observation on treatment, are summarised.

Listings are also provided for ECGs using the normal ranges in [Table 7](#).

**Table 7 ECG Normal Ranges**

AZ Test Name	Outside AZ cardiac SKG reference range lower limit if	Outside AZ cardiac SKG reference range upper limit if	AZ Unit
PR	<100	>240	msec
QRS	<70	>120	msec
QT	<300	>450	msec
QTcF	<300	>450*	msec
HR	<45	>120	BPM
RR	<500	>1333	msec

\*Cut-off values for categorical analyses recommended by ICH E14

BPM = Beats per minute, Msec = milliseconds

#### 4.2.1.8 Other Safety Assessments

##### 4.2.1.8.1 Definitions and Derivations

###### Maximum Tolerated Dose Evaluation (applicable to Substudy 1 Part A only)

See Section 6.6.5 of the CSP for the definition of a DLT. For reporting purposes, the DLTs are as approved and documented at the Safety Review Committee meetings.

After the escalation phase is completed, DLT rates at each dose level are estimated by isotonic regression (Ji et al, 2010). The weighted least squares regression model conditional on monotonic non-decreasing DLT rates with increasing dose and use the empirical (observed) DLT rates at each dose level as responses and sample sizes at each dose level as weights, along with the Pool Adjacent Violators Algorithm (PAVA) to estimate the DLT rate at each dose level using available software (eg, Cytel EAST or the function pava from the R package ‘ISO’). Given the DLT estimates for each dose level, the MTD is selected from all tried dose levels that have not been previously declared to be unsafe with a “de-escalate to the previous lower dose and the current dose is never used again due to unacceptable toxicity” (DU) decision according to the mTPI-2 decision table. With this constraint, the MTD is determined as the dose level with the DLT estimate closest to the target toxicity level of CC%.

In the case of dose levels with estimated toxicity of equal distance (tied dose levels) from the target toxicity of CC%, the following approach is used (Ji et al, 2010): among all tied dose levels the highest dose level with target toxicity  $\leq$  CC% is selected, unless all tied dose levels have estimated toxicity  $>$  CC%, in which case the lowest dose level is selected.

If no DLTs are observed meaning the MTD is unable to be concluded, the maximum per protocol dose will be used.

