- 6. At the discretion of the Sponsor, dose escalation may be stopped before an MTD is reached. In this case, the doses for evaluation in the dose-expansion parts (Part B and Part C) may be chosen based on an assessment of available PK, PD, safety, or efficacy data.
- 7. The MTD will be determined by isotonic regression analysis applied to DLT rates observed during dose escalation using the mTPI-2 method (Guo et al, 2017).

The mTPI-2 employs a simple beta-binomial Bayesian model. Decision rules are based on calculating the UPM of three intervals corresponding to underdosing, proper dosing, and overdosing in terms of toxicity. The underdosing interval corresponds to a dose escalation, overdosing interval corresponds to a dose de-escalation, and proper dosing interval corresponds to staying at the current dose. Given an interval and a probability distribution, the UPM of that interval is defined as the probability of the interval divided by the length of the interval. The mTPI-2 design calculates the UPMs for the multiple equal toxicity intervals, and the one with the largest UPM implies the corresponding dose-finding decision. The design for the dose-escalation part of the Substudy 1 uses a target DLT rate of % and an equivalence interval of (%, %) for dose-escalation/de-escalation decisions as well as MTD determination. A dose level will be considered unsafe, with no additional participants enrolled at that dose level, if it has an estimated 95% or more probability of exceeding the target DLT rate of (ie, P [DLT > 60 % data] > 95%) with at least 3 DLT-evaluable participants treated and evaluated at that dose level. In Table 16 dose escalation/de-escalation decision rules are computed based on the above information.

Dose-escalation decisions guided by the mTPI-2 design with the targeted DLT rate p_T and the equivalence interval (EI) = p_T . The table lists the decisions for up to 9 participants treated at a given dose. The column in this table represents the number of participants enrolled at the dose, and the row represents the number of DLTs at the same dose. The dose-escalation decisions are as follows: E: Escalate to the next higher dose; S: Stay at the current dose; D: De-escalate to the previous lower dose and marking the current dose and its higher doses as unacceptably toxic so that they will never be used again in the remainder of the trial.

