10.6.7 Dose Expansion

Part B

The 2 dose expansion levels will be chosen based on peripheral target engagement and non-overlapping PK in order to evaluate intra-tumoural PD activity and help determine the RP2D. One dose expansion level will be the MTD/HPDD and one dose expansion level will be lower than the MTD/HPDD. Each dose level will enrol approximately 20 participants with NSCLC or MSS-CRC (enrolling approximately 10 participants in each tumour type). Expansions may open either in parallel or sequentially at Sponsor's discretion. Expansions may start before the MTD/HPDD has been determined.

Part C

The two efficacy expansions will be determined based on emerging data from Part A and/or Part B and may include two indications at a single dose level or one indication at two dose levels. If the RP2D cannot be adequately determined from Part B and additional data (eg, efficacy) is required to guide RP2D determination, then two dose levels in one indication will be investigated. If the RP2D is determined at the end of Part B, RP2D will be evaluated in two indications. Each efficacy expansion will enrol up to approximately 40 participants which may include up to 10 participants from the relevant Part B expansion. An interim analysis will take place after 20 participants (further details in Section 10.9.5).

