10.6.9 Definition of maximum tolerated dose

The MTD will be selected from all tried dose levels that have not been previously declared to be unsafe with a DU decision according to the mTPI-2 decision table. With this constraint, the MTD will be determined as the dose level with the DLT estimate closest to the target toxicity level of ...

In the case of dose levels with estimated toxicity of equal distance (tied dose levels) from the target toxicity of %, the following approach will be used (Ji et al, 2010): among all tied dose levels the highest dose level with target toxicity % will be selected, unless all tied dose levels have estimated toxicity %, in which case the lowest dose level will be selected.

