## 2 CHANGES TO PROTOCOL PLANNED ANALYSES

The following changes have been applied to this version of the SAP and are pending update in the protocol:

- The end of study definition in CSP section 4.4 will change from last IP dose to first IP dose, “The end of study is defined as 18 months after the last enrolled participant received his/her first dose of study IP or when the sponsor stops the study, whichever occurs first.”

- The definition of screen failures, in CSP section 5.4, will change in the protocol. Screen failures are patients who have been enrolled but failed to meet the study inclusion/exclusion criteria.
- At the completion of Substudy 1 Part A, all appropriate data will be presented to answer the primary analysis endpoint which will evaluate Dose Limiting Toxicities (DLTs) and determine the MTD. This deviates from the protocol which suggests all data will be presented. Presenting data only applicable to the primary endpoint of Part A, ensures the question is sufficiently answered in a timely manner, and prevents other data not needed for this endpoint being analyzed too early and too often during the study which could have a detrimental affect trial integrity.

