##### 3.3.7.1 Dose escalation: mTPI-2

###### Part A: Substudy 1

The Modified Toxicity Probability Interval-2 (mTPI-2) employs a simple beta-binomial Bayesian model (Guo et al 2017). The posterior density of the toxicity probability is divided into multiple intervals with equal length. These intervals are categorized as underdosing (below), proper dosing (equivalent), and overdosing (above) in terms of target toxicity. The underdosing interval corresponds to a dose escalation, overdosing corresponds to a dose de-escalation, and proper dosing corresponds to staying at the current dose. The design for the dose-escalation phase of the study uses a target Dose Limiting Toxicity (DLT) rate of **[REDACTED]**% and an equivalence interval **[REDACTED]** for dose-escalation/de-escalation decisions as well as MTD determination. A dose level is considered unsafe, with no additional participants enrolled at that dose level, if it has an estimated 95% or more probability of exceeding the target DLT rate of **[REDACTED]**% (i.e.,  $P [DLT > [REDACTED]\% | \text{data}] \geq 95\%$ ).

For specific dose escalation rules, refer to CSP Section 10.6.6.1.3.

For dose escalation (Part A) cohorts of at least 3 and up to 9 evaluable participants are required for each dose cohort (unless unacceptable toxicity is seen before 3 evaluable participants). The total number of participants will depend on the number of non-evaluable participants and the number of dose escalations necessary in order to declare MTD/RP2D. More patients may also need to be enrolled to a dose level if toxicity is observed. It is anticipated that approximately up to 5 dose-escalation cohorts of up to 9 evaluable participants may be included resulting in an overall total of up to approximately 45 participants.

The dosing cohorts are grouped depending on the starting dose they are planned. The starting dose for this study is 300 mg with the maximum dose set at 3000 mg.

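### With no DLTs, the SAP's fallback dose is not limited to doses given, so after a sponsor stop below 3000 mg it names a dose with no participants

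*SAP*

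**What the plan says.** SAP 4.2.1.8.1 estimates the DLT rate at each dose by isotonic regression (PAVA) and takes as MTD the level whose estimate lies nearest the target. The candidates are restricted: "the MTD is selected from all tried dose levels that have not been previously declared to be unsafe". Among levels equally far from the target, the highest one at or below target is chosen, or the lowest if all are above it. The section then ends: "If no DLTs are observed meaning the MTD is unable to be concluded, the maximum per protocol dose will be used".

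The maximum is a fixed number in SAP 3.3.7.1: "The starting dose for this study is 300 mg with the maximum dose set at 3000 mg". Protocol 6.1.1 also lists 3000 mg as the top dosage level.

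Protocol 10.6.9 carries the same restriction, "The MTD will be selected from all tried dose levels that have not been previously declared to be unsafe", and has no exception for zero DLTs. Protocol 10.6.6.1.3 item 6 adds: "At the discretion of the Sponsor, dose escalation may be stopped before an MTD is reached". It sets no dose that must be reached first, and leaves the expansion doses to a review of PK, PD, safety or efficacy data.

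SAP section 2 opens its list of departures with "The following changes have been applied to this version of the SAP and are pending update in the protocol". None of its three bullets concerns the zero-DLT rule. One of them says the Part A data are presented "to answer the primary analysis endpoint which will evaluate Dose Limiting Toxicities (DLTs) and determine the MTD".

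**The concern.** The closing sentence of SAP 4.2.1.8.1 drops the limit to tried doses that governs the rest of the section. When escalation has reached 3000 mg this does no harm: the sentence matches the MTD/HPDD pairing in Protocol 10.6.7 ("One dose expansion level will be the MTD/HPDD and one dose expansion level will be lower than the MTD/HPDD"), and the only question is whether 3000 mg should be called the MTD or the HPDD. When the sponsor stops lower with no DLT, the sentence names 3000 mg although no participant has had it.

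There is also an unstated precedence. With zero DLTs the tie rule already gives an answer, the highest tried dose. The closing sentence has to be read as overriding it, but the SAP does not say so, and the protocol has no matching text.

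At stake is the stated conclusion of the Part A primary analysis, whose purpose in SAP section 2 is to determine the MTD. That conclusion should be a dose with data behind it. No participant's dose is at stake.

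**Working it through.** The plan states no figure to reproduce here. The check is to run the SAP's own algorithm with zero DLTs and compare its answer with the fallback.

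**Inputs.** The 300 mg start and 3000 mg maximum are from SAP 3.3.7.1. The minimum of 3 DLT-evaluable participants per level and the maximum of 9 are from Protocol 10.6.6.1.3. The DLT target and equivalence interval are redacted, so targets of 20%, 25%, 30% and 33% were assumed, with an interval of target ±5 points. The intermediate levels of 1000 mg and 2000 mg are illustrative.

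**Step 1: zero DLTs.** Every observed rate is 0/n = 0, so every PAVA estimate is 0 and all tried doses are equally far from the target. All lie below it, so the tie rule returns the highest tried dose. The fallback returns 3000 mg whatever was tried.

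| Doses tried (mg) | Tie rule | Fallback | Fallback ÷ highest dose given |
|---|---|---|---|
| 300 | 300 | 3000 | 3000/300 = 10 |
| 300, 1000 | 1000 | 3000 | 3000/1000 = 3 |
| 300, 1000, 3000 | 3000 | 3000 | 3000/3000 = 1 |

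The tie-rule results are the same with 3 or 9 participants per level and at all four targets. A stop at 2000 mg would give 3000/2000 = 1.5. The two rules agree only if 3000 mg was given.

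**Step 2: one DLT instead of none, stopping at 1000 mg.**

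- One DLT at 1000 mg, with 3 participants at 300 mg and 3, 6 or 9 at 1000 mg: the estimates at 1000 mg are 1/3 = 0.333, 1/6 = 0.167 and 1/9 = 0.111, against 0 at 300 mg. The algorithm selects 1000 mg each time.
- One DLT at 300 mg, with 3, 6 or 9 participants there and 0/3 at 1000 mg: the two levels are pooled to 1/6 = 0.167, 1/9 = 0.111 and 1/12 = 0.083. They tie below target, so 1000 mg is selected each time.

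These results also hold at all four targets. A single DLT therefore keeps the answer at a tried dose, while none moves it to 3000 mg.

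**Step 3: how the case arises.** With a Beta(1,1) prior and the assumed intervals, mTPI-2 says escalate at 0/3 through 0/9. A zero-DLT stop below 3000 mg therefore needs a discretionary decision under item 6. The plan gives no basis for its probability, and none is claimed.

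**Step 4: information at the named dose.** The exact one-sided 95% upper bound on the DLT rate after 0/n is 1 − 0.05^(1/n): 63.2% for 0/3 and 28.3% for 0/9. With n = 0 it is 100%, that is, no information.

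**The case against.** The strongest reply is that the sentence already says the MTD could not be concluded, so it does not call 3000 mg the MTD, and that it never says what the dose will be used for. SAP 4.2.1.8.2 bases the MTD evaluation on the DLT-evaluable population and specifies only DLT counts by dose level, so no planned table would print 3000 mg as a result. The SAP is to be read together with the protocol, and item 6 covers the early stop. On the ordinary route, zero DLTs lead to 3000 mg, where the sentence is sound.

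Much of this stands, and it keeps the point minor. Expansion doses after an early stop come from Protocol 10.4.1, 10.6.6.1.3 item 6 and 10.6.7, not from this sentence. The by-dose table would show that nobody received 3000 mg. The missing object of the sentence is a real ambiguity.

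It does not remove the defect. Specifying the population and a table does not redefine a maximum that SAP 3.3.7.1 fixes at 3000 mg, and no text defines it as the highest dose reached. Item 6 says how expansion doses may be chosen, not what the Part A MTD evaluation reports. Since section 2 makes determining the MTD the Part A question, the natural use of the fallback dose is as the answer to it.

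**Conclusion.** The concern holds, as a minor error in a stated rule. On a path the protocol permits (no DLT and a sponsor stop below 3000 mg), the SAP followed literally names a dose with 0 participants, contrary to its own tried-dose limit and to Protocol 10.6.9. The departure is not listed in SAP section 2. The named dose exceeds the highest dose given by a factor of 3000/d, at most 10. If 3000 mg was given, the factor is 1 and only the label is unclear.

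The conflict does not depend on the redacted target or on the intermediate dose levels, which serve only as examples. It does rest on reading the maximum as 3000 mg, as SAP 3.3.7.1 and Protocol 6.1.1 state. The consequence is a reported conclusion out of line with its own DLT table; no participant's dose is affected.

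**What to change.** Replace the closing sentence of SAP 4.2.1.8.1 with:

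> If no DLTs are observed, the tie rule is not applied, the MTD is reported as not reached, and the highest dose level administered with at least 3 DLT-evaluable participants is reported as the highest dose evaluated (as the HPDD only if 3000 mg was administered).

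Add a bullet to SAP section 2 recording this as a change from Protocol 10.6.9, and carry it into 10.6.9 at the next protocol update. Under this rule a zero-DLT stop reports 300 mg if only that level was evaluated, 1000 mg if escalation ended there, and 3000 mg only if it was given.

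The cost is one sentence, one bullet and one protocol line. It needs no new data and changes nobody's dose.
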